6.6.4 Sample Collection

One representative web space, according to the grading of signs and symptoms of *T. pedis*, must be classified as at least moderate to be designated as the Target Sampling (or target lesion) web space.

Subjects who have both feet affected, will have samples collected from each foot separately. Subjects that have one foot affected and the other foot unaffected, sample will only be collected from the affected foot. Indicate on the CRF if samples were collected from Left and/or Right foot.

For Microbial Sampling

If one foot is moderate and the contralateral foot is less than moderate the less than moderate foot will also be sampled.

For Drug Product Application

Both feet are treated even if one foot is not affected

Baseline Web space ISGA Grading	Microbial Sampling	Drug Product Application
Clear	No	Yes
Almost Clear	Yes, if contralateral is moderate	Yes
Mild	Yes, if contralateral is moderate	Yes
Moderate	Yes	Yes
Severe	Yes	Yes

Detailed instruction for sample collection and processing are in Table 3 below.

Table 3 Microbiological Samples

	Onsite KOH	Routine Mycology (Fungal Culture & KOH At Central Lab)	Molecular Diagnostics (e-swab)
Day 1 (Baseline -Prior to dose)	Target Sampling Web space	Target Sampling Web space	Target Sampling Web space
1hour after dose			Affected Web space other than Target Sampling Web space
Day 2			Previously not sampled affected Sampling Web space. If not available, then previously not sampled unaffected space.
Day 3			Previously not sampled affected Sampling Web space. If not available, then previously not sampled unaffected space.
Day 7		Target Sampling Web space	Target Sampling Web space
Day 14			Target Sampling Web space
Day 28		Target Sampling Web space	Target Sampling Web space

Throughout the study, continuous monitoring of concomitant medications, therapies and AEs will occur.

6.7 Study Drug Product Administration

All subjects will have a single application of their assigned test article applied by study personnel at the baseline visit. Details of test article preparation are in the Study Operation Manual, in brief, there is a vial with [REDACTED] in an aqueous gel vehicle. Then approximately 0.5 ml of the test article will be applied to each foot covering the toe web spaces, on and around the toe nails as well as the plantar and lateral aspects of the foot. The product will be allowed to air dry.

6.8 Concomitant medication and Excluded Therapy

Usage of prescription or over the counter topical or systemic medications will be reported during the subject's participation in the study. The use of anti-fungal or antibacterial treatments in the past 4 weeks is an exclusion criterion.

6.9 Investigational Product

The test product will be applied by the Investigator or study personnel at the investigational site. Each subject will have a single application of approximately 0.5 ml of the test article applied to each foot. Both affected and unaffected feet will be treated covering the web spaces, toes, toe nails as well as the plantar and lateral aspect of both feet. The product is formulated as a suspension in a low viscosity aqueous gel. The three dose groups are:

- Cohort 1 dose 10^6 /ml CFUs of [REDACTED]
- Cohort 2 dose 10^7 /ml CFUs of [REDACTED]
- Cohort 3 dose 10^8 /ml CFUs of [REDACTED]

The cohort 1 dose is comparable to the dose that has been shown to be effective against cutaneous fungal infection of amphibians. It has been estimated that the density of bacteria on normal skin is approximately $1 \times 10^5/\text{cm}^2$. At our highest dose of 10^8 CFUs/ ml applying 0.5 ml to each foot, this volume will cover approximately 500 cm^2 . The cohort 1, 2, and 3 doses then we would be adding 10^3 CFUs, 10^4 CFUs, 10^5 CFUs / cm^2 , respectively.

The doses in this trial are comparable to the doses used in the study of other topical live bacterial products. An ammonia oxidizing bacterium has been used in Phase 2 trials to treat acne at a dose of $10^9/\text{ml}$ (Aobiome Inc. patent #9738870), a coagulase-negative *Staphylococcus* at a dose of $10^7/\text{ml}$ CFUs (Williams and Gallo 2017) has been used in atopic dermatitis patients, and a strain *P. acnes* has been applied to the face of acne patients at a dose of $10^8/\text{ml}$ CFUs. (<https://www.clinicaltrials.gov/ct2/show/NCT03450369?term=Naked+Biome&rank=2>).

Each of the three groups will have 4 subjects. After the first cohort has completed their day 7 visits, if no significant tolerability or safety issues identified the second cohort will be enrolled. After the

second cohort has completed the day 7 visits and if no significant tolerability of safety issues is identified the third cohort will be enrolled.

6.10 Treatment Compliance

All subjects will receive only a single application of the test article applied at the investigational site by designated study personnel. This will allow for well document compliance, Investigator or designee will record the time, date and dose of drug product administration. Data Analysis and Statistical Consideration.

6.11 General Statistical Considerations

As this is an open label safety and tolerability trial all of the collected data will be presented in listings, tables, and figures in a descriptive fashion.

Primary Objective:

Evaluate the safety and tolerability of DBI-001 in patients with Tinea pedis

Secondary Objective:

Evaluation of presence or persistence of [REDACTED] of DBI-001 following a single application of DBI-001.

Effect of a single application of DBI-001 on the abundance of *T. rubrum*

Effect of a single application of DBI-001 on the signs and symptoms of interdigital T. pedis.

6.12 Analysis of Data for Objectives

- a. Primary Objective: Evaluation of presence or persistence of [REDACTED] following a single application of DBI-001.
- b. Secondary Objective: Effect of a single application of DBI-001 on the abundance of *T. rubrum*.
- c. Exploratory Objectives: Effect of a single application of DBI-001 on the signs and symptoms of interdigital T. pedis.

6.13 Analysis Populations

All subjects treated will be included in the analysis

6.14 Sample Size Determination

As there is no formal statistical analysis planned there were no assumption made in selection of the sample size.

7. ASSESSMENT OF SAFETY

7.1 Safety Evaluations and Criteria

Upon completion of the day 7 visit by the first cohort, the Medical Monitor and Investigator will review the safety results and determine if the trial is to proceed with dosing the second cohort. The same process will be completed upon completion of Day 7 for Cohort 2 to determine if Cohort 3 will be enrolled.

As detailed in section 6.6.3, local tolerability will be evaluated by recording the severity of the signs of *T. pedis* as well as the signs and symptoms of local tolerability on treated areas not involved with *T. pedis*. In addition, adverse events will be documented.

7.2 Adverse Event

An AE is any untoward medical occurrence in a subject administered a pharmaceutical product, which does not necessarily have a causal relationship with the treatment. An AE can be any unfavorable and unintended sign (e.g., including an abnormal laboratory finding), symptom, or disease temporally associated with the use of the study drug product, whether or not it is considered to be study drug product related. This includes any newly occurring event or previous condition that has increased in severity or frequency since the administration of study drug product (treatment-emergent).

7.3 Serious Adverse Event

A serious adverse event (SAE) is any AE, occurring at any dose level and regardless of causality that:

- Results in death.
- Is life-threatening: Life-threatening means that the subject was at immediate risk of death from the reaction as it occurred, (i.e., it does not include a reaction which hypothetically might have caused death had it occurred in a more severe form).
- Requires inpatient hospitalization or prolongation of existing hospitalization.
- Results in persistent or significant disability/incapacity.
- Is a congenital anomaly/birth defect.

- Is an important medical event: an important medical event is an event that may not result in death, be life-threatening, or require hospitalization but may be considered an SAE when, based upon appropriate medical judgment, it may jeopardize the subject and may require medical or surgical intervention to prevent one of the outcomes listed in the definitions for SAEs. Examples of such medical events include allergic bronchospasm requiring intensive treatment in an emergency room or at home, blood dyscrasias or convulsions that do not result in inpatient hospitalization, or the development of drug dependency or drug abuse.
- A hospitalization for an elective procedure will not be considered a SAE

7.4 Unexpected Adverse Event

An unexpected AE is an AE that is not reported in the Investigator's Brochure (IB).

7.5 Relationship of Adverse Events to Study Drug Product

The following classifications should be used when evaluating the relationship of AEs and SAEs to the investigational drug product.

1. **None**: No relationship between the experience and the administration of study drug product; related to other etiologies such as concomitant medications or subject's clinical state.
2. **Unlikely**: The current state of knowledge indicates that a relationship is unlikely.
3. **Possibly**: A reaction that follows a plausible temporal sequence from administration of the study drug product and follows a known response pattern to the suspected study drug product. The reaction might have been produced by the subject's clinical state or other modes of therapy administered to the subject.
4. **Probably**: A reaction that follows a plausible temporal sequence from administration of the study drug product and follows a known response pattern to the suspected study drug product. The reaction cannot be reasonably explained by the known characteristics of the subject's clinical state or other modes of therapy administered to the subject.
5. **Definitely**: A reaction that follows a plausible temporal sequence from administration of the study drug product and follows a known response pattern to the suspected study drug product and can be confirmed with a positive re-challenge test or supporting laboratory data.

Severity:

1. Mild: Awareness of sign or symptom, but easily tolerated
2. Moderate: Discomfort enough to cause interference with normal daily activities
3. Severe: Inability to perform normal daily activities
4. Life-threatening: Immediate risk of death from the reaction as it occurred

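### Section 7.5 has no fitting causality grade for a new reaction: Possibly, Probably and Definitely all require a known response pattern

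*Combined protocol and SAP*

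**What the plan says.** Section 7.5 opens with "The following classifications should be used when evaluating the relationship of AEs and SAEs to the investigational drug product", so the scale covers serious and non-serious events alike. The five grades are None, Unlikely, Possibly, Probably and Definitely.

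- None: "No relationship between the experience and the administration of study drug product; related to other etiologies such as concomitant medications"; in short, something else caused the event.
- Unlikely: what is currently known points against a relationship.
- Possibly: plausible timing "and follows a known response pattern to the suspected study drug product. The reaction might have been produced by" some other cause.
- Probably: plausible timing, and the event "follows a known response pattern to the suspected study drug product. The reaction cannot be reasonably explained by the known characteristics"; in short, nothing else accounts for it.
- Definitely: plausible timing, and the event "follows a known response pattern to the suspected study drug product and can be confirmed with a positive re-challenge test"; laboratory evidence may stand in for re-challenge.

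Section 7.4 recognises that new events may occur, and ties them to the Investigator's Brochure: "An unexpected AE is an AE that is not reported in the" Brochure. Neither 7.4, 7.5 nor 8.2 says how to grade causality when no pattern is known.

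The Synopsis (Adverse Events) makes the investigator's causality assessment part of the description of each AE. Section 6.4.2 names causality among the features of unusual AEs that may lead to discontinuing the study. Before the first escalation, section 7.1 says that "the Medical Monitor and Investigator will review the safety results and determine if the trial is to proceed with dosing the second cohort". A second review of this kind precedes Cohort 3.

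**The concern.** A known-pattern condition presupposes that reactions to the product have already been described. For this organism, sections 1.1 and 1.2 cite in-vitro and amphibian work and its presence on healthy human skin. Section 6.9 supports the doses with amphibian data and other sponsors' products. No observed human reaction to DBI-001 is reported. Section 2.1 names only what might happen: worsening of T. pedis, impetigo, cellulitis, and irritation from the sampling detergent, which is not a reaction to the product.

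Safety and tolerability is the primary objective, and the trial is open label with 4 men per cohort and no control arm. A causality grade pushed down by its definition cannot be corrected by comparison with vehicle. It stays in the AE record that informs the escalation review and the later reading of the trial.

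**Working it through.** No arithmetic applies. The plan gives no figure on this point, so the check is to run test events through the five definitions.

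**Event A: plausible timing, no other explanation, no known pattern.**

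| Grade | What it needs | Met? |
|---|---|---|
| None | Attribution to another cause | No: there is none |
| Unlikely | Knowledge pointing against a relationship | No: absence of knowledge is not evidence against |
| Possibly | Timing and known pattern; another cause might account for it | No: fails on pattern |
| Probably | Timing and known pattern; no other reasonable explanation | No: fails on pattern alone |
| Definitely | Timing, known pattern and confirmation | No: fails on pattern, whatever the confirmation |

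Of the 3 related grades, 3 require the known pattern. Of all 5 grades, 0 fit Event A. With no unassessable grade, the investigator must either set the definition aside and choose a related grade, or fall back on None or Unlikely.

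**Event B: plausible timing, another cause possible but not established, no known pattern.** Possibly is the natural grade, and only the known-pattern condition blocks it.

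**Event C: plausible timing and a known pattern.** The scale works as intended, and Possibly and Probably are separated by whether another cause could explain the event.

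Event C shows that the known-pattern condition does not help to rank the related grades, because all three share it. Another explanation separates Possibly from Probably, and confirmation marks out Definitely. The condition acts only as an entry test for being called related at all.

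**After deleting the condition from Possibly and Probably.** Event A meets Probably, Event B meets Possibly, and Event C is graded as before. The order of the grades is unchanged.

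**The case against.** The strongest case on the other side is that the plan does not act on the causality grade alone, and most of this stands. Section 7.2 defines an AE whether or not it is thought related, and section 7.3 defines an SAE regardless of causality. Local tolerability, the primary endpoint in section 4.2.1, is scored with no causality filter. The review in section 7.1 covers the safety results as a whole, and the investigator is one of its two reviewers. Section 6.4.3 lets the sponsor stop dosing new subjects over any safety concern. No endpoint or escalation threshold is defined on related AEs.

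Four stronger readings are tempting but not supported:

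- *The scale directs new reactions to be coded as unrelated.* It does not. Event A fails None and Unlikely as well; under-grading is the likely result of having no fitting grade, not an instruction.
- *Unexpected and related are close to mutually exclusive.* Section 7.4 ties unexpectedness to the Investigator's Brochure, whereas section 7.5 refers to a known pattern. The documents do not equate the two; an event absent from the Brochure might still fit a reaction anticipated in section 2.1.
- *Definitely is out of reach because nothing could confirm it.* A single application (section 6.10) rules out re-challenge within the trial. But swabs are scheduled at baseline, at 1 hour and at every follow-up visit, with central-laboratory culture and KOH on Days 1, 7 and 28 (Tables 2 and 3). These might serve as supporting laboratory data.
- *The chance of seeing a reaction among four men measures the defect.* That is the chance that an event occurs at an assumed rate. It says nothing about misgrading or a changed decision.

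The Investigator's Brochure was not available and may describe further reactions, which would narrow the affected set. The text between sections 7.5 and 8.2 was also unavailable, so any reporting rule there that depends on relatedness could not be checked.

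None of this supplies a fitting grade for Event A.

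**Conclusion.** The point holds as a defect in the causality definitions. A plausibly timed, otherwise unexplained new reaction cannot receive any of the 3 related grades and has no proper place among all 5. The likely consequence is a causality grade set too low, in a field recorded for every AE and listed as a consideration for study discontinuation. The event itself is not lost, and the documents do not show that an escalation decision would change.

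The size is definitional, since nothing in the documents allows an estimate of how many events would be affected. The conclusion assumes that investigators apply section 7.5 as written and that reactions may occur beyond those already described. It is strongest for reactions outside both section 2.1 and the Brochure. The change should be made: the rule is wrong as written and cheap to repair.

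**What to change.** In section 7.5 and the AE form instructions:

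- **Possibly:** delete the known-pattern condition, leaving plausible timing with another cause also possible.
- **Probably:** delete it likewise, leaving plausible timing and no reasonable explanation from clinical state or other therapy.
- State that a known pattern counts as supporting evidence for a relationship and is not required for these two grades. Definitely can stay as it is, because a new reaction can then reach Probably.

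Optionally, confirm in section 7.1 that each cohort review covers all AEs whatever their causality grade. The present wording does not restrict it, so this is a clarification.

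The cost is a few words and some more AEs graded possibly or probably related, including some due to other causes. No visit, sample or subject number changes.

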8.2 Other Required Safety Assessments

A clinically significant worsening from Baseline of any abnormal study assessment, such as laboratory test, physical examination, or vital signs, should be considered an AE and recorded accordingly. If possible, a diagnosis for the clinically significant study assessment should be provided by the Investigator (e.g., urinary tract infection or anemia). In the absence of a diagnosis, the abnormal study assessment itself should be listed as the AE (e.g., bacteria in urine or decreased hemoglobin).

An abnormal study assessment is considered clinically significant if the subject has one or more of the following related to the abnormal study assessment:

1. Concomitant clinical signs or symptoms.
2. Further diagnostic testing or medical/surgical intervention.
3. Discontinued from the study.

Repeat testing to determine whether the result is abnormal, in the absence of any of the above criteria, does not necessarily meet clinically significant criteria. The determination of whether the study assessment results are clinically significant must be made by the Investigator.

9. SPECIAL REQUIREMENTS AND PROCEDURES

9.1 Study Monitoring

The Clinical Monitor and/or the Sponsor representative will arrange to visit the Investigator sites at regular intervals during the study. The monitoring visits must be conducted according to the applicable International Conference on Harmonization (ICH) and Good Clinical Practice (GCP) guidelines to ensure protocol adherence, quality of data, drug accountability, compliance with regulatory requirements, and continued adequacy of the investigational site and its facilities. During these visits, eCRFs and other data related to the study will be reviewed and any discrepancies or omissions will be resolved. The Clinical Monitor will be given access to study relevant source documents (including medical records) for purposes of source data verification.

During and/or after completion of the study, quality assurance officers named by DermBiont or the regulatory authorities may wish to perform on-site audits. The Investigator is expected to cooperate with any audit and aid and documentation (including source data) as requested.

9.2 Audits and Inspections

The Investigators and clinical sites will permit study related monitoring, audits, IRB/IEC review, and regulatory inspections as requested by FDA, DermBiont or designee, including direct access to source data/documents (i.e., original medical records, laboratory reports, hospital documents, progress reports, signed Informed Consent Forms (ICFs), etc.) in addition to eCRFs.

9.3 Data Quality Control and Quality Assurance

The Investigator is responsible for ensuring the study is conducted according to the protocol, Code of Federal Regulations (CFR), GCP, and applicable regulatory requirements. The responsibilities outlined in these documents along with the identification that a signed informed consent must be obtained prior to a subject participation in the study.

9.4 Confidentiality

To maintain subject privacy, all eCRFs, banked study samples, study drug accountability records, study reports and communications will identify the subject by the assigned subject identification number. The Investigator will grant monitor(s) and auditor(s) from DermBiont or designee and regulatory authority(ies) access to the subject's original medical records for verification of data gathered on the eCRFs and to audit the data collection process. The subject's confidentiality will be maintained and will not be made publicly available to the extent permitted by the applicable laws and regulations.

All information regarding the investigational product supplied by DermBiont to the Investigator is privileged and confidential information. The Investigator agrees to use this information to accomplish the study and will not use it for other purposes without consent from DermBiont Inc. It is understood that there is an obligation to provide DermBiont with complete data obtained during the study. The information obtained from the clinical study will be used towards the development of the investigational product and may be disclosed to regulatory authority(ies), other Investigators, corporate partners, or consultants as required.

9.5 Subject Rights

Study subjects can withdraw their consent to have their clinical samples banked even after the sample has been shipped to the clinical laboratory. A study subject should contact their Investigator or the Investigator's designee and ask for his/her sample to be withdrawn from the bank and destroyed. For samples that have been partially analyzed the remaining sample will be destroyed but the clinical site and DermBiont shall be entitled to retain and use any research results obtained prior to the withdrawal of consent.

